COMIRB Protocol

COLORADO MULTIPLE INSTITUTIONAL REVIEW BOARD
[name] [contact] [contact]

Protocol Version 3, 07/09/2015

Project Title: Aspiration in Acute Respiratory Failure Survivors

Principle Investigator: [name] MD

I. Hypothesis and Specific Aims

We hypothesize that the BSE assessment of swallowing certain consistencies will provide the most accurate diagnosis of aspiration.

A. Specific Aim #1: To develop a BSE-based non-invasive clinical prediction rule (CPR) that will accurately and efficiently diagnose aspiration in ARF survivors.

B. Specific Aim #2: To identify abnormalities in laryngeal structure and swallowing physiology that are associated with aspiration in ARF survivors.

Study Design: Prospective cohort study of patients with acute respiratory failure who require mechanical ventilation for more than 48 hours.

Inclusion Criteria:

1. Admission to an ICU.
2. Mechanical ventilation with an endotracheal tube for greater than 48 hours.

Exclusion Criteria:

1. Age < 18 years
2. Contraindication to enteral nutrition administration.
3. Pre-existing or acute primary central or peripheral neuromuscular disorder
4. Pre-existing history of dysphagia or aspiration.
5. Pre-existing head and neck cancer or surgery.
6. Presence of a tracheostomy.
7. Coagulopathy resulting in uncontrolled nasal or pharyngeal bleeding.
8. Unable to participate due to altered mental status
9. Extubated for greater than 72 hours.
10. Inability to obtain informed consent from patient or an appropriate surrogate.
11. Pregnancy
12. Imprisoned at the time of admission, anytime during the hospitalization, or anytime during the follow up period

First, a SLP will perform a comprehensive BSE on each ARF survivor.

Subsequently a second blinded SLP/investigator will perform the FEES to determine whether aspiration is truly present. The FEES examination will also identify abnormalities associated with aspiration.

For Aim #1: Primary Outcome Variable: Aspiration (PAS score of ≥ 6) on the FEES with any of the five feedings. A PAS score of ≥ 6 includes patients with both silent and non-silent aspiration.

Statistical analysis: Recursive partitioning or Classification and Regress Tree (CART) analysis creates a tree that asks a series of yes/no questions, taking the user down different branches depending on the answers. At the end of each branch will be an estimated probability of outcome.

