Speech language pathologists (SLPs) determine when ARF survivors can resume oral feeding.¹¹ Based on our national survey, SLPs commonly rely upon the bedside swallow evaluation (BSE) to provide feeding recommendations for ARF survivors.¹¹ The BSE consists of a comprehensive history and physical examination followed by assessment of the patient's ability to swallow foods and liquids of different consistencies. SLPs do not routinely order or perform gold standard tests such as a videofluoroscopic swallow study (VFSS) or flexible endoscopic swallow study (FEES).¹¹ This is in part due to appropriate safety concerns about transporting critically ill patients to radiology for a VFSS and the lack of equipment or expertise to perform the FEES.¹¹ In patients with stroke or head and neck cancer, diagnostic CPRs have been developed that detect aspiration based on specific components of the BSE.¹²⁻²² Due to differences in the reasons for aspiration, CPRs for these patients are unlikely to be effective for ARF survivors.^{12-14;16;20} As a result, there are no BSE-based diagnostic non-invasive CPRs that SLPs can use to provide feeding recommendations for ARF survivors.

Using recursive partitioning analysis (RPA), we will develop an effective diagnostic CPR to accurately detect aspiration in ARF survivors.

RPA has been previously used to create clinically useful CPRs including: identifying patients with chest pain that require hospitalization and selecting trauma patients that benefit from a cervical CT scan.^{23;24} Based on our preliminary data, we hypothesize that the BSE assessment of swallowing certain consistencies will provide the most accurate diagnosis of aspiration. We propose to conduct a multi-center study that will enroll ARF survivors within 72 hours after extubation. First, a SLP will perform a comprehensive BSE on each ARF survivor. Subsequently a second blinded SLP/investigator will perform the FEES to determine whether aspiration is truly present (Figure 1).

In ARF survivors, the mechanisms responsible for aspiration are also relatively unexplored.^{25;26} Though many mechanisms may contribute to aspiration in ARF

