After enrollment, the research coordinator should complete the demographic information on the Case Report Forms. No fields on the Case Report Forms should be left blank. The research coordinator should also contact and the SLP who will perform the BSE, and the second SLP who will perform the FEES. The research coordinator should arrange a specific time that the BSE and FEES will be performed.

Screening and recruitment techniques:

Every new ICU admission receiving mechanical ventilation will be screened, wherein an established treatment relationship exists. This will include but not be limited to admissions from the ED, wards, and operating room. We will also assess patients transferred from outside hospitals. The enrollment window for these patients will include the time during admission at the outside hospital and during transfer.

The research coordinators or site PI will meet with the new incoming groups of ICU residents as part of their unit orientation. During this time, the residents will be alerted to each of the study inclusion and exclusion criteria. We would also recommend developing printed laminated cards with important study related and contact for the housestaff and other key members of the ICU teams. Each day, the research coordinator will identify each patient who is endotracheally intubated and receiving mechanical ventilation for at least 48 hours. Patients will then be followed until they are extubated.

At the time of extubation, the patient by definition meets inclusion criteria for the study. At this point the patient should be entered into the screening log in one of several ways

1. If they meet a permanent exclusion criteria, they should be entered as be excluded from the study
2. If they meet a potentially transient exclusion (like altered mental status), they should be followed for up to 72 hours after exclusion to determine if the exclusion criteria resolves. If it resolves they should approached for enrollment
3. If the patient meets no exclusion criteria, they should be approached about study participation.
4. If they agree to participate and sign the consent form then they are enrolled into the study.
5. If they decline to participate, then they should be entered as an excluded patient.

Informed consent:

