Next, a SLP will perform a comprehensive BSE on each ARF survivor, and a second blinded SLP will perform the FEES to determine whether aspiration is truly present. The order of the BSE and FEES exams will be randomized. The reason for the random order of the tests is that after several swallows, a patient who has not eaten orally in several days or weeks will start to do better as the system "wakes up". If the BSE always precedes the FEES, it might lead to a false result – it would show more aspiration on the BSE than the FEES. But it won't be because the BSE was showing a false positive; in fact it is just that the patient started to improve by the time he got the second exam.

2. Bedside Evaluation:

The BSE protocol should be performed within 24 hours from the time that the informed consent was signed. The BSE protocol will be performed in the same order and the amount of each bolus delivered in the exact manner for all patients. Unless there are medical restrictions (due to femoral lines, sacral wounds, etc), all BSEs should be performed in a sitting position. The SLP will document the patient position that the BSE was

performed.

Part 1: Initial Assessment: The SLP will review the subject's medical record and become knowledgeable with the patient's medical history. The patient should be seated with the head of the bed as elevated as possible. A physical exam of the aerodigestive system will be performed including respiratory rate; saliva formation; lip seal; tongue movement, strength, and coordination; palate movement, gag reflex; cough reflex; and voice quality/dysphonia. In addition, the SLP will also determine cough strength in L/min using a peak flow meter (HealthScan, Cedar Grove, NJ).

Part 2: Standardized consistency testing: The SLP will then administer five standard consistencies.¹⁰⁶ Some consistencies will be tested twice with different amounts. In general, the bolus should be administered with a medicine cup. A straw should only be used for the 3 ounce water test and the 2 ounce patient controlled trials.

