Boluses will be administered from lowest to highest aspiration risk: 1) $\frac{1}{2}$ tsp, then 1 tsp ice chips , 2) 1 tsp of nectar thick liquids, then 3 tsp of nectar thick liquids, 3) a 2 ounce patient controlled administration of nectar thick liquids, 4) 1 tsp of pureed solids (applesauce), then 10 mls of pureed solids (applesauce), 5) 5 mls of thin liquids (water or milk),15 mls of thin liquids (water or milk), and a 2 ounce patient controlled administration of thin liquids and 6) $\frac{1}{4}$ of a graham cracker.¹⁰⁷ The patient will be instructed to chew the graham cracker before swallowing. In order to limit the complexity and duration of our consistency testing, honey-thick liquids will be excluded from the protocol.

The SLP will wait for 10 seconds following the completion of each individual trial before recording the results for that consistency. The following adverse outcomes (coughing/choking, change in breath sounds, and change in voice quality, throat clearing, or change in pulse oximetry recording by > 10%) will be recorded after each trial.

If the clinician feels it is unsafe to continue with the next bolus consistency, the protocol can be stopped at any time.

Coughing/choking: Dichotomized as a single cough or choking sound within 10 seconds after diet administration (yes/no).

Change in breath sounds: Breath sounds will be assessed before and 10 seconds after the examination by either auscultating over the larynx at the thyro-cricoid space during quiet breathing or listening to the patient's breathing without a stethoscope. The SLP will record whether they used a stethoscope or not to listen for change in breath sounds. Patients will be classified as "gurgling" or "non-gurgling." Gurgling is a low/medium-pitched rattling sound on inhalation or exhalation.¹⁰⁸

Change in vocal quality: Baseline vocal quality will be assessed initially and dichotomized as normal/abnormal. Any transition from normal to abnormal vocal quality during feeding will be recorded.

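### Exam order is randomised but only the FEES examiner is declared blinded, so a BSE done second has no stated protection from the FEES result

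*Combined protocol and SAP*

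**What the plan says.** All references are to the combined protocol and SAP.

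- **Order.** Study Procedures, in the paragraph after the baseline list: "The order of the BSE and FEES exams will be randomized". The reason given is that swallowing improves with use, so that a worse BSE followed by a better FEES would not mean a false-positive BSE: "in fact it is just that the patient started to improve by the time he got the second exam". No allocation ratio is stated.
- **Fixed-order wording that remains.** The synopsis and the Significance section both say "First, a SLP will perform a comprehensive BSE on each ARF survivor", with the FEES to follow. Item 2 (Bedside Evaluation, Part 3) lets the diet advance before the FEES on the strength of the BSE, which presupposes that the BSE came first.
- **Blinding.** Study Procedures has one speech-language pathologist (SLP) do the BSE "and a second blinded SLP will perform the FEES to determine whether aspiration is truly present". Item 3 (FEES examination) specifies that this second examiner is blind to the BSE findings. No section says that the BSE examiner is blind to the FEES.
- **Access to information.** Of the BSE examiner, item 2, Part 1 says: "The SLP will review the subject's medical record and become knowledgeable with the patient's medical history". FEES findings may go to the treating team on request (end of item 3). The consent talking points say that the patient may watch the FEES and that its results are shared with the doctors.
- **Analysis.** The statistical sections for Aims 1 and 2 plan no stratification, adjustment or sensitivity analysis by exam order.

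**The concern.** The declared blinding fits a BSE-first sequence, where the examiner who goes second is always the one doing the FEES. Once order is randomised, the safeguard covers one sequence and leaves the other open.

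The exposed data are the index test. Several BSE findings are matters of judgement: a change in voice ("Any transition from normal to abnormal vocal quality during feeding will be recorded"), gurgling breath sounds, the pass/fail call on the 3-ounce water test, and the yes/no aspiration item in the summary of the BSE form. BSE findings are the raw material of the Aim 1 prediction rule and of the accuracy estimates for each consistency. An examiner who knows the FEES result would tend to rate towards it, and the BSE would then look more accurate than it is in practice, where no FEES result is at hand.

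The reference side is better protected: its examiner is declared blinded, the whole FEES is recorded, and the videos are shared between sites for scoring.

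**Working it through.** The plan states no figure on this point, so the check is mainly a comparison of sections.

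**1. Protection by sequence.**

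| Sequence | Second examiner | Blinding declared? | Possible routes to the first result |
|---|---|---|---|
| BSE then FEES | FEES SLP | Yes, to the BSE results | Chart review, but covered by the declaration |
| FEES then BSE | BSE SLP | No | Chart review; treating team, if it asks; patient, if they watched |

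Both examiners are told to review the chart, so the only difference between the rows is the declaration.

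**2. Would the planned analysis show the problem?** Ten-fold cross-validation builds each tree on nine parts of the data and tests it on the tenth. All ten parts contain FEES-first patients rated in the same way. If those ratings lean towards the FEES, the held-out ratings lean equally, and the estimated misclassification rate carries the same optimism.

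**3. Direction.** Review bias would raise agreement between BSE and FEES. The improvement that the protocol expects works differently. In FEES-first patients it would make the later BSE look cleaner than the FEES, which lowers BSE sensitivity. The two effects oppose each other in that group, so the net direction is not known.

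**4. Can a size be given?** It would need the share of BSE ratings altered by knowledge of the FEES, which the documents do not give, and a base accuracy. The natural base is the thin-liquid row of Table 1 (sensitivity 38%, specificity 75%, PPV 60%, NPV 55%). Among all two-by-two tables with at most the 26 pilot patients, only one reproduces that row: 8 aspirators with 3 positive and 8 non-aspirators with 6 negative.

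- 3/8 = 37.5%; 6/8 = 75%; PPV 3/(3 + 2) = 60%; NPV 6/(6 + 5) = 54.5%.
- Exact 95% intervals: about 9 to 76% for sensitivity and 35 to 97% for specificity.

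A projected bias would therefore be hypothetical in both inputs, and none is given here.

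**5. What a table by order could show.** Inputs: 225 patients (sample size section); aspiration in 44% (Significance) to 50% (pilot data). Assumptions: 1:1 order and both exams complete in everyone. Early stopping of the bolus series would widen the intervals.

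- Aspirators per order: 225 × 0.44 / 2 = 49.5 to 225 × 0.50 / 2 = 56.25.
- Non-aspirators per order: 225 × 0.50 / 2 = 56.25 to 225 × 0.56 / 2 = 63.
- 95% half-width = 1.96 × √(p(1 − p)/n).
- Sensitivity 38%: 1.96 × √(0.38 × 0.62 / 49.5) = 13.5 points; with n = 56.25, 12.7 points.
- Sensitivity 50%: 13.9 and 13.1 points.
- Specificity 75%: 1.96 × √(0.75 × 0.25 / 63) = 10.7 points; with n = 56.25, 11.3 points.

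That is about 11 to 14 points per order. Power to detect 38% against 58% sensitivity between orders (two-sided 5%) is about 51 to 57%.

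**The case against.** The strongest reply is that the harm is speculative. The treating team must first ask for the FEES result. It must then reach the chart or the BSE examiner within the roughly 4 hours between exams, and it must then sway a judged sign. No section places FEES results in the chart. Two different SLPs do the exams, signs are recorded after each bolus, and each form is completed before its examiner leaves the ICU. Cough within 10 seconds, an oximetry change above 10% and peak cough flow leave less room for judgement. All of this stands, and it limits the point to a missing safeguard. None of it is a rule on disclosure, and the patient who watched the FEES is a route that does not depend on the chart.

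A second reply is that randomisation already deals with order. It balances the expected improvement between the two sequences, although it does not remove it. It does nothing for blinding, and it is what creates the FEES-first group.

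A third is that a table by order has little power and cannot tell unblinding from improvement. That is right, so the table should be optional. It also means that the gap is better closed before data collection, since later analysis could not repair it.

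A fourth is that withholding a FEES result could clash with safety, since the BSE examiner gives further boluses and makes diet recommendations. This also stands: masking must not block safety communication.

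**Conclusion.** The point holds as a gap in the blinding of the index test, together with order wording that contradicts itself. It should be fixed, and the fix is a cheap improvement. It rests on the text alone: randomised order in Study Procedures, blinding declared for one examiner only, and sentences in the synopsis, Significance and Bedside Evaluation that still put the BSE before the FEES.

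The size is unknown. A reader might infer more in two ways, and the documents support neither:

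- **That FEES results do reach BSE examiners.** No leak is shown; only unguarded routes are.
- **That BSE accuracy will be overstated overall.** Review bias would push that way, but the expected improvement by the second exam could push sensitivity the other way, and no figure for either is available. Nothing can be said about the size of any effect on the tree.

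The precision figures for a table by order depend on the assumed 1:1 ratio and complete exams.

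**What to change.** 1. **Mask in both directions.** State in Study Procedures and in items 2 and 3 that each examiner is masked to the other exam's study results, in either order, until their own case report form is complete. Ask the patient and staff not to tell the examiner the result, and log any disclosure. Leave the treating team's access and any safety communication unchanged; a disclosure made for safety is logged, not prevented.
2. **Reconcile the order wording.** Bring the synopsis, the Significance section and the diet-advance sentence into line with the randomised order. For that sentence, the sponsor need only clarify how it applies under each order; no clinical rule is proposed here. State the allocation ratio and add a form field for the assigned order. The dates and times already on the forms usually give the order performed, but not the order assigned.
3. **Optional.** Report BSE sensitivity and specificity by randomised order with 95% intervals, as description only. Note the half-width of about 11 to 14 points per order, and that the table cannot separate unblinding from improvement between exams. A non-significant difference should not be read as no effect.

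**Cost.** Some wording, a form field, a disclosure log and one more step for the coordinator, who already has this task: "The research coordinator should arrange a specific time that the BSE and FEES will be performed". No extra staff are needed, since two SLPs are already used. The downside is that examiners see the other exam's results a few hours later.

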3. Our nationwide survey of SLPs identified current practices to detect aspiration in ARF survivors.¹¹ We designed, validated, and distributed a survey to 1,966 SLPs working in an inpatient setting. Each survey included questions concerning SLP staffing and availability, and methods used in the diagnosis and treatment of dysphagia and aspiration. A total of 836 SLPs completed their survey (43%), 801 of whom were actively practicing. This survey represents the largest published study to date of SLP practices for ARF survivors.

4. There is currently no uniformly used diagnostic CPR to detect aspiration in ARF survivors.¹¹ Only 29% of hospitals have formal guidelines for when critical care providers should consult SLPs in the evaluation of ARF survivors. Most SLPs performed the BSE on average 24 hours after extubation. Importantly, the majority of SLPs (60%) only use the BSE to identify aspiration in ARF survivors. Gold standard tests (VFSS and FES) are not commonly used, and there is significant geographic variability in their use (Figure 4). VFSS and FEES are also more available and more utilized at university hospitals when compared to community hospitals (p < 0.01).

5. We already have enrolled 26 ARF survivors in Aim #1 without any adverse events. A total of 50% of ARF survivors had evidence of aspiration on FEES evaluation. The diagnostic accuracy of each individual assessment of

swallowing foods and liquids of different consistencies appears to be poor for detecting true aspiration (see Table 1). *These data demonstrate feasibility to complete the studies in Aim #1.* By combining specific components of the BSE, we anticipate that we will be able to develop a more accurate diagnostic CPR for aspiration.

6. In ARF survivors, abnormalities of laryngeal function and swallowing physiology are associated with aspiration (Aim #2 data). At Boston University Medical Center, 59 ARF survivors who required mechanical ventilation for at least 48 hours underwent FEES examination including laryngeal structure and swallowing physiology assessment. Upper airway abnormalities were common including: laryngeal edema, vocal cord immobility, and vocal cord granuloma formation. Vocal cord granulomas were associated with severe dysphagia or aspiration ($p = 0.04$). This work has been submitted for publication and demonstrates the feasibility to complete the studies in Aim #2.

OBJECTIVES

Table 1: BSE accuracy for aspiration with different consistencies

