Part 3: Three Ounce Water Swallow Test (3-WST): During the standardized 3-WST, patients receive three ounces of water and are instructed to drink the entire amount, via cup or straw, completely and without interruption (the cup can be held to the patient's mouth by the SLP).^{74;76;109} The 3-WST will be scored as pass/fail. Criteria for failure of the 3-WST are: the inability to drink the entire amount, coughing or choking up to 1 minute after completion, or the presence of a wet-hoarse vocal quality.

At this point the SLP will document their diet recommendations, and whether further invasive testing (MBSS or FEES) is indicated.

Subsequently, the SLP can perform additional testing including specific maneuvers. The results of these additional tests will be recorded in the CRF. The SLP will then document their diet recommendations that include the knowledge gained from the additional testing. Again the SLP will document whether further invasive testing (MBSS or FEES) is indicated.

Based on these recommendations, the patient will be allowed to advance their diet prior to the performance of the FEES, if indicated.

The coordinator should make sure that the BSE CRF is completely filled out before the SLP who completed the test leaves the ICU.

The BSE form for consistency testing is attached as Appendix.

3. FEES examination: The SLP will review the subject's medical record and become knowledgeable with the patient's medical history. The FEES examination will be performed by a second SLP who is blinded to the results of the BSE. The FEES should be performed within approximately 4 hours of the BSE.

Similar to the BSE, the patient should be seated with the head of the bed as elevated as possible. At the discretion of the SLP/investigator, Afrin and Lidocaine spray can be administered into the nasal passage before the laryngoscope is inserted. The use of these medications will be noted in the case report form.

Part 1: First the SLP will perform and videotape the examination of the upper airway. Velar closure, base of the tongue retraction, laryngeal elevation, right and left vocal cord/arytenoid mobility, right and left pharyngeal wall medialization, epiglottic retroflexion, granuloma formation, and upper airway edema will be assessed.

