APPENDIX: Case Report Forms

Part 1: BSE Direct Physical Examination

Facial symmetry	Normal	Asymmetric	Not Done	
Lip seal/strength	Complete seal	Reduced Seal/ Weak	Not Done	
Lip movements	Normal	Slow, uncoordinated	Not Done	
Tongue strength/ ROM	Normal/complete	Weak/Reduced	No movement	Not Done
Tongue movements	Normal	Slow, uncoordinated	Not Done	
Dentition	Adequate	Missing teeth	Dentures	Edentulous
Saliva	Normal	Drools at times	Drools constantly	Not Done
Palate/velar elevation	Adequate	Incomplete	Not Done	
Baseline voice	Normal	Aphonic	Hoarse	Wet, gurgly
Baseline Breathing sounds	Normal	Wet	Hoarse/noisy	Stridorous
Respiratory rate (count breaths for 20 seconds and then multiple by 3)	_____ (breaths/min) or Not performed			
Volitional cough	Strong	Weak	Absent	Not done
Volitional cough with peak flow meter	_____ (liters/min) or Not performed			

Part 2: Bolus administration

Study ID:	Date:	Time:
-----------	-------	-------

Note: Determine signs and symptoms of aspiration within 10 seconds after swallowing

Ice Chips (1/2 tsp) Bolus given: YES NO	Signs of Aspiration Can check 1,2, 3, 4, or 5 signs  No aspiration or  Cough/Choking  Throat Clearing  Change in voice  Change in Breath sounds YES NO	Oral Phase Can check 1,2, 3, or 4 signs  Normal or  Prolonged/Slow/Delayed/Cued  Disorganized  Weak (oral residual)  Other impairment Explain: <hr/>	Hyolaryngeal excursion Can check 1, 2, or 3 signs  Normal or  Delayed/Slow  Reduced  Multiple swallows
Ice Chips (full tsp) Bolus given: YES NO	Signs of Aspiration Can check 1,2, 3, 4, or 5 signs  No aspiration or  Cough/Choking  Throat Clearing  Change in voice  Change in Breath sounds YES NO	Oral Phase Can check 1,2, 3, or 4 signs  Normal or  Prolonged/Slow/Delayed/Cued  Disorganized  Weak (oral residual)  Other impairment Explain: <hr/>	

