If yes complete the following table.

Patient stopped 1+ times?	Patient failed to drink the entire amount?	Cough/Choking?	Change in Voice??	Change in Breath Sounds?	No signs of aspiration
 Yes  No					

RESULTS of 3 oz water test? PASS FAIL

Pass= drinks the entire amount without stopping (use your judgment), and without coughing, choking during or immediately after completion.

Fail = does not finish the total amount, stops 1+ times (for more than a few seconds), or has overt signs of aspiration immediately after swallowing

SUMMARY OF CLINICAL EXAM

Results:

Dysphagia detected? Yes/no (oral or pharyngeal)

Aspiration detected? Yes/no

Diet texture recommendations (circle one)

Solids: regular (NDD3) mechanical (NDD2) puree (NDD1) npo

Liquids thin nectar honey npo

Part 4: Scoring Sheet for the FEES Testing

R 21 FEES Evaluation Form		
Study ID:	Date:	Time:

MAKE SURE THE ENTIRE EXAMINATION IS VIDEOTAPED

Afrin spray used: **YES** **NO**

Topical lidocaine used: **YES** **NO**

Velar Closure (hiss like a snake)	 Complete  Incomplete  N/A
Base of Tongue Retraction (Paul is tall)	 Present  Absent  N/A
Right Vocal Cord/Arytenoid Mobility	 None  Mild  Moderate  Severe  N/A
Left Vocal Cord/Arytenoid Mobility	 None  Mild  Moderate  Severe  N/A
Glottic Closure (breath hold, cough, phonation)	 Complete  Incomplete  N/A
Laryngeal Elevation/ Arytenoid lift (glide with an “eee”)	 Present  Absent  N/A
Right Pharyngeal Wall Medialization	 Complete  Reduced  Absent  N/A
Left Pharyngeal Wall Medialization	 Complete  Reduced  Absent  N/A

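### The bolus voice sign is defined only as a normal-to-abnormal change, so an abnormal baseline voice cannot score on it; the form uses a different rule, and the 3-ounce water test has its own text-versus-form mismatch

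*Combined protocol and SAP*

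**What the plan says.** **Bolus trials, protocol text** (Study Procedures, 2. Bedside Evaluation, Part 2). Among the signs noted after each trial are "change in voice quality, throat clearing, or change in pulse oximetry recording by > 10" per cent, alongside cough or choking and breath sounds. The paragraph that defines the voice sign reads: "Baseline vocal quality will be assessed initially and dichotomized as normal/abnormal". It continues: "Any transition from normal to abnormal vocal quality during feeding will be recorded". No rule is given for a patient whose voice is abnormal at the start.

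**Bolus trials, form** (Appendix: Case Report Forms, Parts 1 and 2). Baseline voice has four levels: normal, aphonic, hoarse, or wet/gurgly. Each bolus then has a tick box labelled "Change in voice", with no condition on baseline and no definition.

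**3-ounce water swallow test (3-WST), protocol text** (2. Bedside Evaluation, Part 3). The list of failure criteria ends with "or the presence of a wet-hoarse vocal quality". Baseline is not mentioned.

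**3-WST, form** (Appendix, Part 3). The table asks about "Change in Voice". The fail rule covers not finishing, stopping, "or has overt signs of aspiration immediately after swallowing". A wet-hoarse voice is not named.

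**The concern.** Aim 1 builds its prediction rule from BSE components. The analysis section does not list the predictors, but voice change is one of the signs collected on every bolus. Additional Considerations also plans sensitivity and specificity of the BSE for each consistency. A sign that some patients cannot show, because of how it is defined, is a weaker predictor in those patients for reasons unrelated to swallowing.

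Abnormal baseline voice is plausible in this cohort. Patients are enrolled within 72 hours of extubation, and item 6 of the preliminary data says: "Upper airway abnormalities were common including: laryngeal edema, vocal cord immobility, and vocal cord granuloma formation". The same item reports that granulomas were associated with severe dysphagia or aspiration (p = 0.04). Patients with an abnormal voice may therefore be over-represented among aspirators. That is an inference, since no rate of dysphonia is reported.

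The other signs compensate only in part. The plan also calls for a separate rule for silent aspiration (PAS score 8, which Table 3 describes as no effort to eject). Cough and throat clearing are less likely to help there, so more weight falls on voice, breath sounds and oximetry.

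The text and form also differ, so the same swallow can be recorded differently by two raters who each follow a study document. Two sites enrol, according to Risks and Justifications.

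**Working it through.** The plan states no figure on this point, so there is none to reproduce. The check sets the definitions side by side and then bounds the effect.

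**Step 1. Apply each document to the same patient (bolus trials, voice sign only).**

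| Voice before → after swallow | Protocol text | Form |
|---|---|---|
| Normal → wet | Recorded | Box can be ticked |
| Hoarse → wet | Starts abnormal, so no qualifying transition | Box can be ticked |
| Wet → wetter | No qualifying transition | Box can be ticked, by judgement |
| Aphonic → aphonic | No qualifying transition | Box unticked, same as a true negative |

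The documents agree on the first row. In the second and third they permit opposite entries. In the fourth, a sign that could not be assessed looks the same as one that was absent.

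**Step 2. The same for the 3-WST voice criterion.**

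| Voice before → after | Protocol text | Form |
|---|---|---|
| Normal → wet-hoarse | Fail | Change recorded; fail if judged an overt sign |
| Wet-hoarse → unchanged | Fail | No change, so need not fail on voice |
| Dry hoarse → unchanged | Not a failure on voice | Not a failure on voice |

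The conflict is confined to voices that are already wet-hoarse before the test.

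**Step 3. Bound the effect on the bolus voice sign under the protocol wording.** Let h be the share of aspirators whose baseline voice is abnormal, and s the sign's sensitivity among aspirators with a normal baseline. Then

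sensitivity = (1 − h) × s + h × 0 ≤ 1 − h.

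Inputs:
- N = 225 (Sample Size Calculation and Feasibility).
- Aspiration in 44% (Background, given there as an upper figure) or 50% (preliminary data, item 5, from 26 patients). Aspirators: 225 × 0.44 = 99, or 225 × 0.50 = 112.5.
- h is not in the documents. A range of 20% to 80% is assumed.

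Number who cannot score on the voice sign = N × prevalence × h.

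| Assumed h | Ceiling 1 − h | Of 99 aspirators | Of 112.5 aspirators |
|---|---|---|---|
| 20% | 80% | 19.8 | 22.5 |
| 40% | 60% | 39.6 | 45.0 |
| 60% | 40% | 59.4 | 67.5 |
| 80% | 20% | 79.2 | 90.0 |

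These are ceilings for one sign if every rater follows the protocol text. They are not estimates of what the study would find.

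**Step 4. Can the analysis recover it?** If raters follow the text, voice change is constant (negative) in everyone with an abnormal baseline. A tree that first splits on baseline voice then has nothing left to split on for voice change in that branch. A hoarse-to-wet change that was not written down cannot be restored later.

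**The case against.** The best case for the plan has five parts.

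- *Only one sign is affected.* Every bolus is also scored for cough or choking, throat clearing, breath sounds and oximetry, and the breath-sound item (gurgling or not) may catch wetness after a swallow. This stands. A reader might infer that hoarse patients can never be positive on the bolus trials. The documents do not support that, because only the voice sign is closed to them.
- *The text need not be read narrowly.* Voice change is first listed without a baseline condition, the defining sentence does not say that other changes are ignored, and the form where data are entered has an open box. This is fair, and it means the loss is not certain in practice. It does not remove the problem: the only operational definition is the narrow one, the box has none, and raters may differ.
- *The water test does not fail everyone who is hoarse.* This stands. A reader might infer that the same hoarse patients are forced negative on one predictor and positive on another. The text's criterion is wet-hoarse, so a dry-hoarse patient does not meet it, and the form does not apply it as written. The overlap is at most those already wet-hoarse at baseline.
- *The tree can use baseline voice.* The form collects four levels, and the plan notes that recursive partitioning accommodates interactions without pre-specifying them. This helps if baseline voice is offered as a predictor, which the plan does not say. Step 4 shows the limit.
- *A narrow definition, applied consistently, gives a less informative predictor rather than a biased estimate of the rule's accuracy.* This is correct. The FEES outcome is untouched.

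It is also fair that the 3-WST is presented as a standardized test with cited sources, so changing its criterion is debatable.

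**Conclusion.** The point holds in limited form. Followed literally, the protocol fixes the bolus voice sign at negative for anyone with an abnormal baseline voice, and the form permits a different entry for the same swallow. Separately, text and form give different voice criteria for failing the 3-WST.

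The size is unknown, because the documents report neither how often baseline voice is abnormal nor how often voice changes in such patients. What can be said is conditional: if raters follow the text and a share h of aspirators starts abnormal, sensitivity of the voice sign is capped at 1 − h, from 80% to 20% across the assumed range. The effect on the finished rule is smaller than that cap suggests to whatever extent other signs are positive in the same patients.

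This is a cheap improvement to one candidate predictor. It does not undermine Aim 1. The reason to make it at the measurement stage is that unrecorded changes cannot be recovered in analysis.

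**What to change.** 1. **Bolus definition.** In 2. Bedside Evaluation, Part 2, and on the bolus form, define voice change as a new wet or gurgly quality, or a worsening from the patient's own recorded baseline, using the four levels already on the form.
2. **Aphonic patients.** Code the voice sign as not assessable, not negative. State how the tree handles that category, for example as its own level, and how such a patient is classified in the per-consistency accuracy tables when no other sign is present.
3. **Predictor list.** Name four-level baseline voice as a candidate predictor for Aim 1.
4. **3-WST.** Reconcile the Part 3 text with the form so that one pass/fail voice criterion applies. Which criterion to adopt is for the investigators; this review does not choose.

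The cost is wording in the protocol and form, brief rater training at both sites, and a small not-assessable category to handle in the analysis. No procedure is added.
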